9.4: Interim Analyses and Stopping Rules.....	24
9.5: Outcomes.....	24
9.5.1: Primary Outcome	24
9.5.2: Secondary Outcomes	24
9.6: Data Analyses	24
10. DATA COLLECTION AND QUALITY ASSURANCE.....	25
10.1: Data Collection Forms: Data Type & Personnel Collecting Data	25
10.2: Data Management	25
10.3: Quality Assurance	25
10.3.1: Training	25
10.3.2: Quality Control Committee	26
10.3.3: Metrics	26
10.3.4: Protocol Deviations.....	26
10.3.5: Monitoring.....	27
11. PARTICIPANT RIGHTS AND CONFIDENTIALITY	27
11.1: Institutional Review Board (IRB) Review	27
11.2: Informed Consent Forms.....	27
11.3: Participant Confidentiality.....	27
11.4: Study Discontinuation Understanding.....	28
12. COMMITTEES	28
13. PUBLICATION OF RESEARCH FINDINGS	28
14. REFERENCES	28
15. SUPPLEMENTS/APPENDICES	33
Appendices List.....	33
A. Consent Form	33
B. Data Collection Forms.....	33

C. AE & SAE Forms.....	33
------------------------	----

STUDY TEAM ROSTER

Principal Investigator

[name], PI, Physical Medicine and Rehabilitation, [name]. [contact], [contact], email: [contact]

Co-Investigators

[name], Co-I, *Department Of Exercise and Sports Science*, [name]. [contact], [contact], email: [contact]

[name], Co-I, Department of Physical Medicine and Rehabilitation, [name]. [contact], email: [contact]

[name], Co-I Department of Physical Medicine and Rehabilitation, [name]

Biostatistician

[name], Biostatistician, NC TraCS. [name]. [contact], email: [contact]

Research Assistants

TBD

PARTICIPATING STUDY SITES

Primary Site: EXSS Neurophysiology Lab, [name].

Secondary Site: UNC Medical School, [name].

PRÉCIS

Title: The Effects of Cranial Laser Reflex Technique (CLRT) on Hamstring Flexibility, Strength, and Pain: a pilot study.

Objectives: To assess the acute effect on hamstring flexibility, strength, and pain pressure threshold of a novel laser therapy intervention (CLRT) compared to sham.

Design and Outcomes

This is a randomized, blinded crossover trial with 44 healthy young adults that will compare the acute effects of CLRT to sham laser on hamstring flexibility, strength, and pain pressure threshold (PPT). The primary outcome is hamstring flexibility, which will be assessed by independent examiners using the standard Knee-Extension-Angle (KEA). As secondary outcomes, hamstring strength will be measured using handheld dynamometry (HHD), and PPT with digital algometry. The intervention will consist of low-level-laser stimulation of the hamstring cranial reflex points for an average total treatment time of 30 seconds. A one-week washout period will occur between visits, and participants will have access to usual care throughout the research study. The research study will be conducted at the Neurophysiology Lab at the University of North Carolina and in UNC Medical School, Wing D.

Specific Aim 1: To examine the acute effect of CLRT on hamstring flexibility as measured by the standard 90-90 Knee Extension Angle (KEA) test.

Hypothesis 1: CLRT will increase mean hamstring flexibility immediately after treatment.

Specific Aim 2: To examine the acute effect of CLRT on hamstring strength as measured by handheld dynamometry (HHD).

Hypothesis 2: CLRT will have a neutral to positive effect on hamstring strength.

Specific Aim 3: To examine the acute effect of CLRT on hamstring pain pressure threshold as measured by digital algometry.

Hypothesis 3: CLRT will increase PPT in the hamstrings.

LIST OF ABBREVIATIONS

ADL	Activity of Daily Living
AE	Adverse Event/Adverse Experience
ATP	adenosine triphosphate
CLRT	Cranial Laser Reflex Technique
Co-I	Co-Investigator
CRF	Case Report Form
CRP	Cranial Reflex Point
CTCAE	Common Terminology Criteria for Adverse Events
DHHS	Department of Health and Human Services
DSMC	Data and Safety Monitoring Committee
EXSS	Exercise and Sport Science
FDA	Food and Drug Administration
HHD	Handheld Dynamometry
HIPAA	Health Insurance Portability and Accountability Act
Hz	Hertz
ICF	Informed Consent Form
IDE	Investigational Device Exemption
IRB	Institutional Review Board
KEA	Knee extension angle
LLLT	Low level laser therapy
LTrP	Latent trigger point
mtNO	mitochondrial nitric oxide
mW	miliwatt
NC TraCS	North Carolina Translational and Clinical Sciences Institute
NIH	National Institutes of Health
nm	nanometer
NRS	Numerical Rating Scale
OHRP	Office for Human Research Protections
PBM	Photobiomodulation
PI	Principal Investigator
PID	Participant ID
PPT	Pain Pressure Threshold
PS	Potential subject
SAE	Serious Adverse Event/Serious Adverse Experience
tcPBM	Transcranial Photobiomodulation
UNC	University of North Carolina
UNC-CH	University of North Carolina at Chapel Hill
UP	Unexpected Problem
US	United States

2. BACKGROUND AND RATIONALE

2.1: Background

Hamstring injuries are a common occurrence in many sports that involve sudden or explosive movements, such as jumping and sprinting. Soccer and lacrosse players are especially at risk for these frustrating injuries that have the highest rate of recurrence (12-31%) in sports(1) making prevention and rehabilitation important areas of study. Static stretching is widely performed, even though it may cause a significant loss of strength(2), endurance(3), and explosive performance for 24 hours(4). Latent myofascial trigger points (LTTrPs) are typically asymptomatic neuromuscular lesions that are associated with muscle overload and decreased contractile efficiency and are highly prevalent in the lower extremity(5). Currently no clear consensus exists on the most effective protocols for prevention of hamstring injuries(6), but decreased flexibility and reduced strength are known risk factors for hamstring strain(1) and other musculoskeletal lesions such as lower back pain(7).

Low Level Laser Therapy (LLLT) aka Photobiomodulation (PBM) is the application of low doses of monochromatic coherent light from low powered laser devices to induce a biostimulatory effect in the target tissue. PBM has been shown to be effective for musculoskeletal pain relief and wound healing(8), as well as many other applications (9-14). PBM is anti-inflammatory and reduces oxidative stress, working primarily on the mitochondria in stressed or ischemic tissues. The mitochondria produce nitric oxide (mtNO) that binds to the chromophore cytochrome c oxidase, competitively displacing oxygen leading to oxidative stress and reduced ATP production. Light of suitable wavelength, sufficient irradiance and time when applied to injuries is absorbed by cytochrome c oxidase, displacing mtNO and thereby reducing oxidative stress and increasing ATP production. A cascade of downstream metabolic effects leads to a reduction in inflammatory markers including prostaglandin E2, interleukin 1 β , interferon (α , β , γ), and tumor necrosis factor- α (15-17). Anti-inflammatory and immune-modulatory markers are also upregulated, such as TGF- β 1, IL-4, and IL-10 (18, 19).

Lasers have a long history of use in acupuncture in lieu of needles (20-23). Typically, lower doses (1-4 J/cm²) of laser light are used on specific points to induce a non-local or systemic effect. Laser acupuncture has been shown to be effective in a variety of musculoskeletal conditions such as low back pain and knee pain, and has been shown to have significant effects on brain activation in fMRI studies (24, 25)

Cranial Laser Reflex Technique (CLRT) is a novel complementary and alternative (CAM) medicine intervention for musculoskeletal conditions that incorporates principles of laser acupuncture with chiropractic cranial reflexology(26). Developed in 2006 by [name] (PI), CLRT has been incorporated into clinical practice by hundreds of practitioners around the world. It involves non-invasive laser stimulation of a distinct cranial microsystem discovered by chiropractors(27). It was postulated that these cranial reflexes are similar in nature to acupuncture points and would likewise respond to

photobiomodulation (PBM) from a low level laser (28, 29) (30). Clinical experience by the PI and others confirmed that cranial reflexes are indeed responsive to low doses (0.5-5 J/cm²) of laser light: the length, strength, and pain in a specific muscle could be improved rapidly, even in cases of chronic post-stroke muscle spasms(31). This pilot study will examine the acute effect of this promising intervention on hamstring flexibility and strength in healthy young adults.

2.2: Study Rationale

Preliminary Findings

The Principal Investigator, [name], has 16 years of clinical experience in conservative care of musculoskeletal conditions, specializing in manual manipulation and laser therapy. Since developing CLRT in 2006, he has amassed clinical data and presented numerous case reports from clinical practice demonstrating that CLRT has the ability to modulate muscle tone, strength, and pain. This is the first clinical trial to directly examine these effects of CLRT in human subjects.

Environment and Capabilities of the Research Team

This project will take place at the University of North Carolina School of Exercise and Sports Science Neurophysiology Lab. [name], the PI of this proposed project, is a board-certified chiropractor and postdoc research fellow in the Program on Integrative Medicine in The Department of Physical Medicine and Rehabilitation.

3. STUDY DESIGN

This is a randomized, assessor-blinded, sham controlled crossover study with repeated measures.

First Visit. The research staff will schedule all study visits in the Neurophysiology Lab or other appropriate site in the UNC Healthcare system or medical school. The baseline phase of the first visit will include review of inclusion/exclusion criteria and the components of the study. Those who wish to sign the consent will complete a brief questionnaire on their activity level, history of hamstring injuries, and perceived hamstring tightness.

Randomization/Random Allocation. Subjects who meet the inclusion criteria and give consent will be randomized to one of the following for the first treatment period: 1) active CLRT; or 2) sham laser. At the first intervention visit, the research assistant will enter the subject's assigned ID into an online computer program (selected by study biostatistician) to determine assignment to one of the two periods. The study biostatistician will use computer-generated random numbers to generate the allocation sequence using random blocks of random sizes. The program documents treatment assignment in an un-editable form including a date stamp.

Post Randomization. After randomization, subjects will be asked to complete the three functional hamstring tests: KEA, HHD, and PPT. Subjects will have direct contact with the investigator and research assistant at each visit to facilitate adverse event reporting.

Assessments. KEA: The 90-90 Knee Extension Angle test is a functional assessment designed to assess lower extremity flexibility and is considered the gold standard for hamstring length (32). The participant will be in the supine position on a treatment table. The tested extremity (the right leg in each subject) will be placed in a 90° hip and 90° knee position with the contralateral lower extremity placed flat on the table. A digital inclinometer will be consistently placed at the level of the medial malleoli and the superior pole of the patella. The examiner will maintain 90° of hip flexion. Pelvic position will be monitored by palpation of the anterior superior iliac spine and lumbar spinous processes to maintain a neutral pelvic position. The examiner will passively extend the knee to the point of a "strong, but tolerable stretch," as reported by the subject. The examiner will read the angle of the inclinometer and record the mean value of three attempts. A greater angle indicates greater degree of flexibility.

Hand held Dynamometry (HHD) is currently considered a reliable and valid measurement of peak muscle contraction(33). The subject will be prone on the table with right leg bent to 90°. The tester will place the dynamometer (microFET2; Hoggan Health Industries, Salt Lake City, UT) at the heel of the participant and apply force to the heel, gradually increasing in 3 to 5 seconds. Participants will be instructed to resist the applied force and maximally contract the hamstring muscle against the HHD device. The test ends once they are no longer able to resist the force and the leg begins to move (break point). The investigator will record the mean value of three attempts.

Pain Pressure Threshold (PPT) is a reliable, accurate and valid method for measuring muscle pain sensitivity and response to treatment(34). The digital algometer (FDX, Wagner Instruments, Greenwich, CT) is a hand-held muscle tester with a range of 0–100 lbf that consists of a padded disc with a diameter of 0.5" attached to a microprocessor-control unit that measures peak force (pounds or kilograms). The unit has a digital readout for peak-applied pressure and provides a built-in calibration routine that verifies a valid calibration. In order to determine PPT, the researcher will apply the tip of the algometer to a tender spot in the participant's hamstrings and increase the amount of pressure until the participant verbally informs the researcher when the sensation of pressure became pain. At this point

the algometer is removed and the peak force recorded. The mean of three repeated measures will be reported.

Intervention: CLRT. Subject will don protective eyewear and remain in the prone position. The hamstring reflexes are two lines on the posterior portion of the top of the head, approximately 2 cm long and 2 cm apart, running parallel to the sagittal suture (fig. 1). The posterior end of the reflexes can be located by finding the vertex, or CZ point in the standardized 10-20 EEG system, and moving laterally approximately 1 cm.

Sequence:

The aperture of the laser probe will be placed at point (a), turned on and moved to point (b) at a speed of approximately 2 cm/s. The laser will be turned off and quickly returned to point (a), turned on and moved to point (b) again. This will be repeated for a total of 30 times. The probe will make light contact with the scalp during the powered laser pass, moving aside as much hair as possible.

Device: The treatment device to be used in this study is a Class IIIB 810nm 200mW near-infrared GAAIAS diode laser (THOR Photomedicine Ltd, Great Britain) that is currently marketed in the US. The laser probe is FDA-cleared and classified as a non-significant risk device. The spot size is 0.0364 cm², and the treatment time is 30 seconds. Current best-practice recommendations for laser acupuncture(35) recommend a dosage between 1-4 J/cm² per point. Since the cranial reflex point (CRP) is a line of 2 cm, for the purposes of calculating dosage, we will treat it as a series of 10 connected points each with a diameter of 2mm. With the scanning rate of 2cm/s, each “point” on the line will receive 1/10 of each pass, totaling 3s (out of 30s total) exposure time per point. The dose per point for this intervention is calculated to be approximately **1.65 J/cm²**.

$$\text{Power Density} \left(\frac{J}{cm^2} \right) = \frac{\text{end power}(W) * \text{Time}(s) * \text{energy loss factor} \left(\frac{1}{cm} \right)}{\text{area}(cm^2)}$$

$$= \frac{0.2 W * 3s * 1}{0.0364 cm^2} = 1.65 \frac{J}{cm^2}$$

Random Allocation. At the first intervention visit, the research assistant will enter the subject’s assigned ID into an online computer program that will determine assignment to one of the two treatment periods. Using a random number sequence to generate a permuted block of 2-4, the program ensures

[figure not shown]

Fig.1 Location of bilateral cranial reflexes for hamstrings

equal numbers of subjects in each arm. The program documents treatment assignment in an un-editable form including a date stamp.

Masking. The research coordinator and treating investigator will be unmasked. All research assistants performing the assessments will be masked. Masking will be maintained in the random allocation procedure. The treating investigator will not indicate to subjects or assessor to which period the participant is assigned.

Remuneration. Subjects will receive an Amazon gift card worth \$25 upon completion of the second visit. If the subject completes only the first visit, they will be compensated a prorated amount with a card worth \$15.

The following patient-reported variables will be assessed:

- 1) **Expectation of benefit:** Measured with a modified Borkovec and Nau scale(36). This instrument provides an assessment of credibility of each intervention using an adaptation of a validated credibility scale previously developed for psychological studies for purposes of comparing the two treatment arms. This instrument has been successfully adapted for use in other conditions such as chronic pain and migraine headache. It will be administered after each subject completes the second visit.
- 2) **Perceived value of the intervention** is measured at the end of the active intervention via questionnaire. At the end of the post-intervention phase, subjects will be invited to participate in a brief post-study interview to assess their overall impressions of the treatment.

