7. SAFETY ASSESSMENTS

7.1: Specification of Safety Parameters

Low level laser devices used for the purposes of photobiomodulation or acupuncture are designated by the FDA as “non-significant risk” devices (37). After four decades of research, over 4000 peer-reviewed papers and over 150 Phase III clinical trials, there are no known side effects attached to low level laser therapy (LLLT). Animal studies have shown that lasering the head, or transcranial photobiomodulation (tcPBM), is very safe and causes no thermal or neoplastic changes in the cortex(38). The use of tcPBM has been shown to have promise for treating traumatic brain injury(39-41) and stroke(42-44), as well as enhancing mood(45-47) and cognition(48-52) in humans.

CLRT involves principles and laser dosages very similar to laser acupuncture. Laser acupuncture has been extensively studied and deemed to be safe and effective for certain musculoskeletal conditions(21), especially in long-term follow up (29). No known or anticipated serious side effects from CLRT have yet occurred but minor reactions may include mild delayed onset muscle soreness or headache. Due to the intensity of the laser light, subjects will wear proper eye protection that blocks the specific wavelength of light while lasers are in use.

Based on previous research, no serious side effects are anticipated. The PI will closely monitor all subjects for any adverse events and will report them to the IRB if any arise.

Examples of safety measures include: monitoring subjects for any discomfort related to intervention; reports of cramps, spasms, headache or delayed onset muscle soreness.

7.2: Methods and Timing for Assessing, Recording, and Analyzing Safety Parameters

- 1) Timing: each contact with the subject will be an opportunity to inquire about adverse events.
- 2) Recording: each incidence of an adverse event will be recorded in the case report form in a designated location for this information.
- 3) Analyzing: the PI will be informed of all adverse events and will forward the information to the IRB.

7.3: Adverse Events (AEs) and Serious Adverse Events (SAEs)

Definitions

An adverse event (AE) is any untoward medical occurrence in a subject during participation in the clinical study. An adverse event can include a sign, symptom, abnormal assessment (laboratory test value, vital signs, electrocardiogram finding, etc.), or any combination of these.

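### On its printed inputs the laser dose is about 16.5 J/cm² per point, ten times the stated 1.65 J/cm²

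*Combined protocol and SAP*

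**What the plan says.** The dose is derived in Section 3, Study Design, under Device. The laser is rated at 200 mW, the spot size is 0.0364 cm² and the treatment time is 30 s. The reflex is a 2 cm line, and for dosing "we will treat it as a series of 10 connected points each with a diameter of 2mm". Each point gets one tenth of every pass, "totaling 3s (out of 30s total) exposure time per point". The section cites best-practice guidance for laser acupuncture, said to "recommend a dosage between 1-4 J/cm² per point". It then states: "The dose per point for this intervention is calculated to be approximately" 1.65 J/cm². The equation below that sentence prints 0.2 W × 3 s × 1 over 0.0364 cm² and gives 1.65 J/cm² again.

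The procedure is set out earlier in Section 3, under Intervention and Sequence. One powered sweep runs along the line at about 2 cm/s, and "This will be repeated for a total of 30 times". On anatomy it says "The hamstring reflexes are two lines on the posterior portion of the top of the head". The Précis describes stimulation of the "hamstring cranial reflex points for an average total treatment time of 30 seconds". Section 7.1 adds that "CLRT involves principles and laser dosages very similar to laser acupuncture".

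**The concern.** The printed equation does not give its printed result. The 1.65 J/cm² figure comes directly after the 1-4 J/cm² recommendation and serves to show that the trial's only active intervention conforms to it. A tenfold error would reverse that: the dose would lie above the recommended range, and also above the 0.5-5 J/cm² that Section 2.1 reports from clinical experience with cranial reflexes.

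An IRB member, a reader or anyone repeating the study could not tell which dose was intended or delivered. A second ambiguity adds to this. The text describes two lines, but the calculation gives all 30 s to one 2 cm line.

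**Working it through.** **Inputs (Section 3)**

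- Power: 200 mW = 0.2 W, in the prose and the equation.
- Spot area: 0.0364 cm², in the prose and the equation.
- Exposure per point: 3 s, in the prose and the equation. The procedure supports it: 2 cm at 2 cm/s is 1 s per pass, 30 passes make 30 s, and one tenth is 3 s.
- Energy loss factor: 1, in the equation only. Its unit reads as 1/cm, which would make the result W·s·(1/cm)/cm² = J/cm³ rather than J/cm².

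**The plan's own equation**

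Dose = power × time × loss factor / area = 0.2 × 3 × 1 / 0.0364 = 0.6 / 0.0364 = **16.48 J/cm²**. The stated 1.65 is not reproduced.

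- Against the stated figure: 16.48 / 1.65 = 9.99.
- Against the top of 1-4 J/cm²: 16.48 / 4 = 4.12.
- Against the top of 0.5-5 J/cm²: 16.48 / 5 = 3.30.

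**Other readings of the text**

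| Reading | Calculation | Dose (J/cm²) | Ratio to 1.65 |
|---|---|---|---|
| As printed | 0.6 / 0.0364 | 16.48 | 10.0 |
| 30 passes shared by two lines (1.5 s per point) | 0.3 / 0.0364 | 8.24 | 5.0 |
| 2 mm point as the area (π × 0.1² = 0.0314 cm²) | 0.6 / 0.0314 | 19.10 | 11.6 |
| 2 mm point, passes shared | 0.3 / 0.0314 | 9.55 | 5.8 |

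None gives 1.65, and all exceed 4 J/cm². They depend on the printed power, time and loss factor, so they are not bounds.

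**What would give 1.65, changing one input only**

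- Time: 1.65 × 0.0364 / 0.2 = 0.300 s, not 3 s.
- Power: 1.65 × 0.0364 / 3 = 0.020 W, not 0.2 W.
- Area: 0.6 / 1.65 = 0.364 cm², not 0.0364 cm². That is a spot 2 × √(0.364/π) = 0.68 cm across, which does not suit a model of 2 mm points. The stated area gives 2 × √(0.0364/π) = 0.215 cm, which does.
- Loss factor: 1.65 × 0.0364 / 0.6 = 0.100, not 1.

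The documents state none of these values.

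**Loss factor that would put the dose within 1-4 J/cm²**

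- Passes per line: 1 × 0.0364 / 0.6 = 0.061 to 4 × 0.0364 / 0.6 = 0.243.
- Passes shared: 1 × 0.0364 / 0.3 = 0.121 to 4 × 0.0364 / 0.3 = 0.485.

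**Dose per pass (0.1 s on each point, loss factor 1)**

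- Stated spot: 0.2 × 0.1 / 0.0364 = 0.549 J/cm². One pass gives 0.55, two 1.10, seven 3.85 and eight 4.40. The range 1-4 therefore corresponds to 2 to 7 passes per line.
- 2 mm point: 0.2 × 0.1 / 0.0314 = 0.637 J/cm². Two passes give 1.27, six 3.82 and seven 4.46, so 2 to 6 passes.

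**The case against.** The best counter-argument concerns the loss factor. Its value appears once, inside a typeset equation, and a factor of 1 makes the term do nothing. A factor of 0.1 gives 0.06 / 0.0364 = 1.648, which rounds to 1.65. A decimal point could have been lost when the protocol was typed or when its PDF was converted to text, and the unbalanced unit shows that this part of the equation is unreliable. This stands as a reason not to declare 16.5 J/cm² the true dose. It does not rescue the text as it reads: no value of 0.1 appears anywhere, and a decimal slip in the result would explain the mismatch equally well.

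The consequences can also be called small. An operator can deliver the treatment from power, speed and number of passes without using 1.65. The probe is described as FDA-cleared and non-significant risk, and Section 5.1 reports similar results from 5 mW to 500 mW. These points limit the claim, since no harm is shown. They do not supply the missing dose justification, which is what the 1.65 figure is there for.

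Whether the passes are per line or shared may be settled by Fig. 1, which is not reproduced in the text available. The shared figures are given for that reason. Even on that reading the printed inputs give five times the stated dose. Finally, several smaller input errors could combine to produce 1.65, so the single-input list is not exhaustive.

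**Conclusion.** The concern holds: the equation is wrong as written. On the printed inputs the dose is 16.48 J/cm² per point, against a stated 1.65, and 4.1 times the top of the cited 1-4 J/cm² range. If the 30 passes are shared between two lines it is 8.24 J/cm², 2.1 times the top. Both figures assume the printed 200 mW, 0.0364 cm², 30 passes at 2 cm/s and a loss factor of 1.

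The division is certain; the true dose is not. If an input is misprinted, the dose may be in range, but the protocol then misstates a treatment parameter. If the inputs are right, the stated dose and the implied fit with the recommendation are wrong. The general comparison with laser acupuncture in Section 7.1 does not rest on 1.65, so it needs only a check. Sample size, randomisation and analysis are unaffected. It should still be corrected before treatment, because it concerns the dose of the only active intervention.

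**What to change.** Before treatment, check power, spot area, exposure time and energy loss factor (value and unit) against the device and the source calculation. State whether the 30 passes are per line or shared. Then take one of three courses:

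1. If an input is misprinted, correct it and recompute the dose.
2. If the inputs are right and the procedure stays, restate the dose as about 16.5 J/cm² per point (8.2 if shared). Remove the implied conformity with 1-4 J/cm², and check that the Section 7.1 comparison still fits this trial's dose.
3. If the inputs are right and 1-4 J/cm² is intended, reduce to about 2 to 7 passes per line at 2 cm/s on the stated spot, or 2 to 6 on a 2 mm point.

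While the equation is open, relabel it: it is headed as power density, but J/cm² is energy density. Carry the reconciled figure into the IRB documents. The choice of dose belongs to the clinical and device team.

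The cost is one device and source check, one recalculation and a protocol amendment, with no extra data or participants. Under the third course the treatment becomes shorter.
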